### Questionnaires, Equipment, and Other Measures.

Participants will be asked to complete questionnaires at baseline (1-Week Pre-quit), Quit Day (1-Week Post-Enrollment), 1-Week Post-Quit Day, 2-Weeks Post-Quit Day, 3-Weeks Post-Quit Day, 4-Weeks Post-Quit Day, 8-Weeks Post-Quit Day, 12-Weeks Post-Quit Day, and 26-Weeks Post-Quit Day. At in-person visits, participants will complete self-report questionnaires on a

tablet computer; and have their expired CO, weight, and height measured in a private room to ensure confidentiality. At remote visits, participants will complete self-report questionnaires on their own device via REDCap or complete them over the phone. Participants completing remote appointments will also be provided with a Bedfont iCO smokerlyzer to measure expired CO. The questionnaire appendix will come from the TTRP IRB 6951.

**Smartphones.** Participants will be guided through the process of downloading the Insight™ smartphone application onto their personal smartphone and will be asked to complete daily EMAs during the 13 week period when they are taking their study medication(s). Those who do not possess a phone that meets the minimum requirements to download the Insight™ app, will be provided with a study phone. The smartphone app home screen will include: 1) a “Call Staff” function/button that automatically calls study staff when participants have problems with the app, and 2) a “Payment” function/button that enables participants to track their current level of compliance with phone-based surveys and level of compensation. At the baseline visit, all participants will receive training about how to use the smartphone app to complete EMAs (i.e., they will watch a “How to Use This App” video) and how to use the “Call Staff” and “Payment” button/options. Participants will be instructed to quit smoking at bedtime or 10:00 pm (whichever occurs first), the night before their scheduled quit day. The app will remind participants about their approaching quit date during each day of the pre-cessation period.

**Varenicline.** All participants will be evaluated by the study physician, and prescribed varenicline (if eligible). Individuals with a history of seizures, allergic reaction to varenicline, endorse current suicidality, and/or those who are pregnant, planning to become pregnant, or breastfeeding will be excluded from the proposed study. As a precaution, individuals who report current cardiovascular disease will require clearance from the study physician or their personal physician to use varenicline. Notably, recent research has indicated that neither varenicline nor NRT increases the risk of serious cardiovascular events. In December 2016, the FDA lifted the boxed warning for varenicline after findings were published from a large clinical trial showing that the risk of neuropsychiatric adverse events associated with varenicline did not differ from the nicotine patch or placebo, and that varenicline was more effective for smoking cessation than the nicotine patch, bupropion, and placebo (the nicotine patch and bupropion were more effective than placebo). As a precaution, female participants will be advised to avoid pregnancy while taking varenicline and to discontinue the medication should they become pregnant. However, the findings of observational research suggests that taking varenicline does not appear to be harmful during pregnancy. During the first (pre-quit) week of the study, participants will continue smoking and begin taking varenicline. Doses are titrated during the first week of medication (days 1-3: 0.5 mg once daily; days 4-7: 0.5 mg twice daily).

**Oral NRT.** Participants randomized to a VAR+N group will be provided with a supply of 2mg/4mg nicotine lozenges or 2mg/4mg gum (depending on participant preference) and instructed to use a piece as directed after they quit smoking, especially when they have the urge to smoke. Participants will be instructed to chew a piece of gum as follows:

Baseline: every 1-2 hours (12-24 per day)

4-Weeks Post-Quit: every 1-2 hours (12-24 per day), and to begin reducing to at least every 2-4 hours (6-12 per day)

8-Weeks Post-Quit: every 2-4 hours (6-12 per day), and to begin reducing to at least every 4-8 hours (3-6 per day)

Additional supply of gum or lozenges will be provided during in-person visits or through the mail. Participants assigned to VAR+N with medication reminders will receive smartphone prompts (through the Insight™ app) (during waking hours) reminding them to use a piece of gum or a

lozenge every 3 hours through 4 weeks post-quit, every 4 hours during post-quit weeks 5-8, and every 6 hours during post-quit weeks 12.

Reminders. Participants assigned to the reminder groups will receive reminders to take varenicline and/or oral NRT as follows:

Varenicline Reminders. Participants will receive varenicline reminders that correspond with the medication schedule. The reminders will provide a message and then ask the participant if they have taken medication. Reminder 2 will only appear if the participant has reported “no” to reminder 1. Reminder 3 will only appear if the participant has reported “no” to reminder 2. On the 3rd reminder the participant will be asked why they did not take their medication.

Pre-Quit Day 1: Only PM reminder (1 white pill (0.5 mg) daily)

Pre-Quit Days 2-3: Only AM reminder (1 white pill (0.5 mg) daily)

Pre-Quit Days 4-7: AM and PM reminders (1 white pill (0.5 mg) in the morning and 1 in the evening)

Day 8 to end of treatment: AM and PM Reminders (1 blue pill (1 mg) in the morning and 1 in the evening)

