**Table 2. Varenicline reminders**

Pre-Quit Day 1 Message	Don't forget to take your Chantix pill tonight!		
Pre-Quit Days 2-3 Message	Don't forget to take your Chantix pill this morning!		
Pre-Quit Day 4-7	Don't forget to take your Chantix pill twice daily (morning and night)!		
Day 8 to end of treatment	Don't forget to take your Chantix pill twice daily (morning and night)!		
AM		PM	
Reminder 1 (30 minutes after Daily Diary)	You were scheduled to take your morning Chantix pill at [INSERT TIME] AM. Have you taken your Chantix pill this morning? (Yes/No)	Reminder 1 (2 hours and 30 minutes after before sleep time)	You were scheduled to take your evening Chantix pill at [INSERT TIME] PM. Have you taken your Chantix pill this morning? (Yes/No)
Reminder 2 (1 hour after Reminder 1)	You were scheduled to take your morning Chantix pill at [INSERT TIME] AM. Have you taken your Chantix pill this morning? (Yes/No)	Reminder 2 (1 hour after Reminder 1)	You were scheduled to take your evening Chantix pill at [INSERT TIME] PM. Have you taken your Chantix pill this morning? (Yes/No)
Reminder 3 (1 hour after Reminder 2)	You were scheduled to take your morning Chantix pill at [INSERT TIME] AM. Have you taken your Chantix pill this morning? (Yes/No)	Reminder 3 (1 hour after Reminder 2)	You were scheduled to take your evening Chantix pill at [INSERT TIME] PM. Have you taken your Chantix pill this morning? (Yes/No)

	
If no: What are the main reasons that you did not take your Chantix pill this morning? (Check all that apply)
 
 
1. I forgot to take it.
 
2. I was away from home.
 
3. I experienced side effects.
 
4. I didn't feel like I needed it.
 
5. I didn't think it is working.
 
6. I have decided not to quit smoking.
 
7. Other
 
		
If no: What are the main reasons that you did not take your Chantix pill this evening? (Check all that apply)
 
 
1. I forgot to take it.
 
2. I was away from home.
 
3. I experienced side effects.
 
4. I didn't feel like I needed it.
 
5. I didn't think it is working.
 
6. I have decided not to quit smoking.
 
7. Other
 

--	--	--	--

NRT Reminder. Participant will receive a message and then be asked if they have used NRT in the past 2, 4, or 8 hours.

Quit Day – 4 Weeks Post-Quit: Reminder every 3 hours

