5 Weeks Post-Quit – 8 Weeks Post-Quit: Reminder every 4 hours

9 Weeks Post-Quit – 12 Weeks Post-Quit: Reminder every 6 hours

[figure not shown]

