**Table 3. NRT reminders**

1. Don't forget to use nicotine gum/lozenges regularly throughout the day! It is recommended that you use a piece of gum/lozenge every 1-2 hour.
 
After you have been smoke free for 6 weeks, taper down to using a piece of gum/lozenge every 2-4 hours and then after being smoke free for 8 weeks, taper down to a piece every 4-8 hours.
	
2.	Have you used a piece of gum/lozenge within the past 2 hours?  No Yes
3.	(If 2 = No) Have you used a piece of gum/lozenge within the past 4 hours?  No Yes
4.	(If 3 = No) Have you used a piece of gum/lozenge within the past 8 hours?  No Yes

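### The oral NRT instructions start the first taper step at 4 weeks post-quit, but the app message sent to one randomised cell starts it after 6 weeks smoke free

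*Combined protocol and SAP*

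**What the plan says.** Three places in section C (Research Design and Methods) govern oral NRT timing.

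- **Oral NRT paragraph**, for both VAR+N cells. From baseline the rate is every 1-2 hours. The next two entries are "4-Weeks Post-Quit: every 1-2 hours (12-24 per day), and to begin reducing to at least every 2-4 hours (6-12 per day" and "8-Weeks Post-Quit: every 2-4 hours (6-12 per day), and to begin reducing to at least every 4-8 hours (3-6 per day". The clock is time since the quit date.
- **Table 3 (NRT reminders)**, the app message. Its opening advice is "It is recommended that you use a piece of gum/lozenge every 1-2 hour". The first step, a move to every 2-4 hours, is introduced by "After you have been smoke free for", and the figure given is 6 weeks. For the second step the figure is 8 weeks and the advice reads "taper down to a piece every 4-8 hours". The clock is time smoke free.
- **NRT reminder schedule**, printed between Tables 2 and 3. The prompt periods are "Quit Day – 4 Weeks Post-Quit: Reminder every 3 hours", then "5 Weeks Post-Quit – 8 Weeks Post-Quit: Reminder every 4 hours", then every 6 hours in weeks 9-12.

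Aim 2 and the text after the Oral NRT paragraph both restrict the NRT prompts to VAR+N participants assigned to reminders. VAR+N participants without reminders have only the Oral NRT paragraph to follow. Nothing in the protocol reconciles 4 weeks with 6 weeks, or the two clocks.

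**The concern.** This is operative dosing text for a study medicine. In weeks 5 and 6 a participant in the VAR+N cell with reminders has been told by staff to start cutting down, while the app still recommends the full rate and puts the cut two weeks later.

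It also bears on Aim 2, which asks whether reminders improve adherence and cessation. For oral NRT that question can be answered only by comparing the two VAR+N cells. The reminder cell differs from its comparator in being prompted, and also in being given a different taper instruction. If NRT use differed between these cells in weeks 5-6, the plan could not say whether prompting or the later taper advice was responsible.

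**Working it through.** The plan states no figure to reproduce. The check is a side-by-side reading with simple date arithmetic.

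| | Oral NRT paragraph | Table 3 app message | NRT prompt periods |
|---|---|---|---|
| Sent to | both VAR+N cells | VAR+N with reminders | VAR+N with reminders |
| Clock | weeks since quit date | weeks smoke free | weeks since quit date |
| Step 1 (to every 2-4 h) | begins at 4 | after 6 | prompts slow after week 4 |
| Step 2 (to every 4-8 h) | begins at 8 | after 8 | prompts slow after week 8 |

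**Participant abstinent since quit day** (the two clocks coincide)

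- Step 1 gap: 6 − 4 = 2 weeks = 14 days, that is days 29-42.
- Share of post-quit treatment: 12 weeks × 7 = 84 days; 14/84 = 16.7%.
- Step 2 gap: 8 − 8 = 0 weeks.

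**Participant who lapses.** Read literally, time smoke free falls behind time since the quit date. Step 1 is then delayed beyond week 6 and step 2 beyond week 8 relative to the Oral NRT paragraph. The protocol does not say whether a lapse restarts the count, so I put no number on this.

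**Do the instructions exclude each other in weeks 5-6?** No. The 4-week entry restates every 1-2 hours as the current rate and asks for a reduction to begin. It sets no date by which every 2-4 hours must be reached; that rate first appears as the current rate in the 8-week entry. Continuing every 1-2 hours in weeks 5-6 is therefore compatible with both texts. A participant who has already cut to every 2-4 hours follows the Oral NRT paragraph but is ahead of Table 3.

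**Which text is out of line?** The prompt periods change after weeks 4 and 8, and Table 4 places visits at weeks 4 and 8. Both agree with the Oral NRT paragraph. Only Table 3 uses 6 weeks or a smoke-free clock.

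**Contact during the gap.** Counselling runs through week 4 and the next scheduled visit is at week 8, so the 14 days fall between visits. Staff follow-up on NRT use is described under Medication Risk Management, without timing.

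**Number affected.** 100/4 = 25, assuming equal allocation to the four cells.

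**The case against.** The best defence is that the instructions describe a gradual taper between weeks 4 and 8, and a step at week 6 lies inside that window. A participant who obeys Table 3 breaches nothing in the Oral NRT paragraph. This stands as far as it goes: the texts overlap and are not opposites. It does not remove the difference in when to start. At the second step both texts name week 8, so Table 3 is not simply giving completion dates for tapers begun earlier.

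Tying the taper to being smoke free could also be deliberate, and 6 weeks could be the intended figure. The prompt periods are imperfect evidence against that, because prompts every 3 hours do not match the every-1-2-hour dose in either text. This also stands. The documents favour 4 weeks without proving it, so the physician should confirm the week as well as the clock.

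Two stronger readings are tempting, and neither is supported.

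- *Table 3 makes the NRT adherence reference unclear in weeks 5-6, so a given number of pieces a day would be scored adherent on one text and not on the other.* The plan defines no oral NRT adherence threshold for any week, and nothing says pieces per day will be scored against a schedule. That gap exists with or without Table 3. The daily counts are also fragile. Table 3 gives none. The Oral NRT paragraph's own counts imply a 24-hour day, so every 2 hours is 24/2 = 12 pieces. Over an assumed 16 waking hours it is 16/2 = 8. A participant using 8 a day would miss the first floor and meet the second.
- *The discrepancy biases the reminder comparison or the abstinence outcomes.* Nothing in the documents shows that it changes NRT use or cessation. The randomised contrast stays valid as a comparison of the reminder package as delivered, which includes this message.

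**Conclusion.** The inconsistency is real and minor. One randomised cell receives two differing start points for the first NRT reduction, on two different clocks. The VAR+N comparison of reminders with no reminders therefore includes a difference in dosing text as well as the reminders themselves.

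For continuous abstainers the difference is confined to the first step. It lasts at most two weeks, because a participant may follow both texts by staying at the full rate. It can last longer, and reach the second step, for those who lapse.

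This rests on three assumptions: allocation is equal; the schedule in the Oral NRT paragraph, which is worded for gum, applies to lozenges as well; and the app displays Table 3 as printed. The missing definition of NRT adherence is a separate matter covering all weeks.

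**What to change.** Use one taper schedule and one clock in both the Oral NRT paragraph and Table 3, with the study physician confirming the week of the first step and the clock. The default is to change Table 3 to 4 weeks and 8 weeks after the quit date, which matches the Oral NRT paragraph, the prompt periods and the visits at weeks 4 and 8. If the physician intends 6 weeks or a smoke-free clock, change the Oral NRT paragraph instead, so that both VAR+N cells receive the same instruction.

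The cost is one edited app message and the matching protocol text, with no added participants, visits or procedures. If enrolment has begun, log the date of the change so that participants who saw the old message can be identified.

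### The NRT reminders in the VAR+N + Reminders cell are not reconciled with the directed NRT regimen, most clearly from quit day to week 4

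*Combined protocol and SAP*

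**What the plan says.** All of the places below are in section C of the protocol.

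- **Directed use (Oral NRT).** The instruction from the start is "Baseline: every 1-2 hours (12-24 per day"). The next step is "4-Weeks Post-Quit: every 1-2 hours (12-24 per day), and to begin reducing to at least every 2-4 hours (6-12 per day"), and the last is "8-Weeks Post-Quit: every 2-4 hours (6-12 per day), and to begin reducing to at least every 4-8 hours (3-6 per day").
- **Who is prompted (Oral NRT).** "Participants assigned to VAR+N with medication reminders will receive smartphone prompts (through the Insight™ app) (during waking hours"). The prompts concern a piece of gum or a "lozenge every 3 hours through 4 weeks post-quit, every 4 hours during post-quit weeks 5-8". The same sentence then gives 6 hours, but for week 12 only.
- **Reminder list (NRT Reminder, after Table 2).** "Quit Day – 4 Weeks Post-Quit: Reminder every 3 hours", then every 4 hours for weeks 5 to 8, then "9 Weeks Post-Quit – 12 Weeks Post-Quit: Reminder every 6 hours".
- **The message (Table 3).** "It is recommended that you use a piece of gum/lozenge every 1-2 hour". The same text tells the participant to move to 2-4 hours after 6 smoke-free weeks and to 4-8 hours after 8. No version by period is given. Follow-up questions ask about use in the past 2, then 4, then 8 hours.
- **Purpose (Study Design).** The prompts are meant to support regular use in line with the directions given. The varenicline reminders are expressly tied to the medication schedule; no such statement is made for NRT.

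**The concern.** The reminder is one of the two randomised factors, and Aim 2 asks whether it improves adherence. Section A motivates it partly by infrequent gum use in earlier trials of bupropion plus gum. For that test to be clean, the reminder should repeat the regimen and add only a cue.

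Here three statements of the NRT schedule differ: the directions, the prompt schedule and the prompt text. The sharpest difference is from quit day to week 4, before any taper, where 3 hours lies outside the directed 1-2 hours. If the prompt sentence is implemented as written, participants in this cell could receive a different NRT instruction from VAR+N participants without reminders. A difference in NRT adherence between those two cells would then mix the effect of being reminded with the effect of being told something different.

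**Working it through.** **Inputs.** Directed intervals and daily counts come from Oral NRT. Prompt intervals come from Oral NRT and the NRT Reminder list. The message comes from Table 3. The directed schedule is worded for gum; I take it to cover lozenges too, as Table 3 does. Waking time is set for each participant (EMA alert settings) and no figure is given, so I assume 16 hours, with a range of 14 to 18.

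**Step 1: reproduce the protocol's daily counts.** Pieces per day = hours / interval.
- 1-2 hours: 24/2 = 12 to 24/1 = 24. Stated 12-24.
- 2-4 hours: 24/4 = 6 to 24/2 = 12. Stated 6-12.
- 4-8 hours: 24/8 = 3 to 24/4 = 6. Stated 3-6.

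All three reproduce exactly, on a 24-hour day. The prompts run only in waking hours, so prompts and uses must be compared over the same number of hours.

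**Step 2: quit day to week 4, with W waking hours.** Prompts = W/3. Directed uses = W/2 to W/1.
- Against the 2-hour end: (W/3)/(W/2) = 2/3 = 67%.
- Against the 1-hour end: (W/3)/W = 1/3 = 33%.

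W cancels, so the ratio does not depend on the assumed waking time. The counts do:

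| W (hours) | Prompts, W/3 | Directed uses, W/2 to W |
|---|---|---|
| 14 | 4.7 | 7 to 14 |
| 16 | 5.3 | 8 to 16 |
| 18 | 6 | 9 to 18 |
| 24 | 8 | 12 to 24 |

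**Step 3: later periods, at 16 hours.**

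| Period | Prompts | Directed uses at start | Directed uses after reduction |
|---|---|---|---|
| Weeks 5-8 | 16/4 = 4 | 8 to 16 (1-2 h) | 16/4 = 4 to 16/2 = 8 (2-4 h) |
| Weeks 9-12 | 16/6 = 2.7 | 4 to 8 (2-4 h) | 16/8 = 2 to 16/4 = 4 (4-8 h) |

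In weeks 5-8 the prompt sits at the sparse edge of the reduced range. In weeks 9-12 it lies inside the reduced range. In both periods it is sparse only against the interval that the participant is leaving.

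**Step 4: the message against the directions.** Through week 4, Table 3 and Oral NRT agree on 1-2 hours. Oral NRT then begins reduction at 4 weeks post-quit, while Table 3 waits for 6 smoke-free weeks. For someone abstinent since quit day that is a gap of 6 - 4 = 2 weeks. It is longer after a lapse, because the two clocks differ. The opening line still recommends 1-2 hours in every period.

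**Step 5: who is affected.** With four cells of equal size, 100/4 = 25 participants.

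**The case against.** The strongest reply is that 3 hours is only how often the app fires. The reminder list speaks of a reminder at each interval, the message itself says 1-2 hours, and a reminder need not fire once per piece. The follow-up questions fit a periodic check: someone using a piece every 1-2 hours can answer yes to the 2-hour question at every 3-hour prompt. Oral NRT also directs use particularly at urges, so use is not purely prompt-driven. Fewer prompts than pieces can be a sensible limit on burden.

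Much of this stands. Prompt frequency alone is a design choice, and one piece per prompt is a reading of one sentence, not observed behaviour. But that sentence can be read as an instruction to use a piece every 3 hours, the protocol does not say that sparser prompting is intended, and the taper mismatch in Table 3 remains on either reading.

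Three stronger inferences are tempting and are not supported.
- A reader might infer that the reminder half of VAR+N is cued less than the other half. The other half receives no NRT prompts. Read as prompt frequency, the reminder cell gets the same directions plus about 5 prompts a day.
- A reader might infer that the VAR+N versus VAR contrast is diluted, or that a null reminder result would mean nothing. Neither follows. Lower use would require participants to anchor on the prompt interval despite the message, for which the documents give no evidence. A null result would still describe the reminder as delivered.
- A reader might divide waking-hour prompts by the printed daily counts. That mixes a waking day with a 24-hour day and overstates the gap.

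**Conclusion.** The inconsistency is real but narrow. It affects the VAR+N + Reminders cell only, about 25 of 100 participants if allocation is equal. From quit day to week 4 the prompt sentence, read as a use interval, implies one third to two thirds of the directed uses; this ratio needs no assumption about waking time. Read as prompt frequency, it implies no reduced instruction, but the directions, prompt schedule and message still need reconciling. The Table 3 taper conflicts with the directions on either reading. Weeks 9-12 add little, and the reference to week 12 alone is clerical, since the reminder list gives weeks 9-12.

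The consequence is that the NRT-adherence part of Aim 2 becomes harder to interpret, because the reminder factor may also carry a different NRT instruction. The varenicline reminders are separate, and varenicline adherence is not affected. The correction is cheap and should be made. I take no view on which interval is right.

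**What to change.** Reconcile the Oral NRT directions, the prompt sentence in that section, the NRT Reminder list and Table 3. In each period (quit day to week 4, weeks 5-8, weeks 9-12), the use interval conveyed by the prompt should agree with the directed interval. This includes when the taper starts and whether its clock is weeks post-quit or weeks smoke-free. The study physician decides which interval stands.

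If prompts are deliberately less frequent than use, state that and the reason, and reword the prompt sentence so that it cannot be read as an instruction to use a piece at the prompt interval. Align the week-12 reference with the weeks 9-12 entry in the reminder list.

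The cost is a protocol wording change and period-specific app messages in place of one text. The Programming paragraph says that the platform allows study-specific messaging to be set up quickly. If participants have already been enrolled, record the date of the change so that the analysis can identify who received which message.
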